### **3.8.2.6 Calcineurin Inhibitor (CNI) Doses**

Calcineurin inhibitors include systemic tacrolimus and cyclosporine. Descriptive statistics will be provided for:

- Number and percentage of subjects who reduced CNI dose
- Number and percentage of subjects who ever discontinued CNI during KD025 treatment period

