7.2. Inclusion Criteria

The inclusion criteria are detailed below:

1. Adult male and female subjects at least 18 years of age who have had allogenic bone marrow transplant or hematopoietic stem cell transplantation.
2. Receiving glucocorticoid therapy and calcineurin therapy or glucocorticoid therapy alone for cGVHD at study entry. Subjects on calcineurin therapy only, without glucocorticoid therapy, are not eligible. Subjects also receiving other therapies thought not to be immunosuppressive (such as extracorporeal photopheresis [ECP]), will be considered for enrollment in this study on a case-by-case basis.
3. Have persistent active cGVHD manifestations, as defined by 2014 NIH Consensus Development Project on Criteria for Clinical trials in cGVHD, after at least 2 months of steroid therapy.
4. No more than 3 prior lines of treatment for cGVHD.
5. Karnofsky Performance Scale of > 40 (see [Appendix E](#)).
6. Adequate organ and bone marrow functions evaluated during the 14 days prior to enrollment as follows:
 - a. Absolute neutrophil count $\geq 1.5 \times 10^9/L$ (without myeloid growth factors within 1 week of study entry)
 - b. Platelet count $\geq 50 \times 10^9/L$ (without transfusion or thrombopoietin or thrombopoietin analogues within 2 weeks of study entry)
7. Adequate safety laboratory values:
 - a. Total bilirubin $\leq 1.5 \times$ upper limit of normal (ULN)

- b. ALT and AST $\leq 3 \times$ ULN
 - c. Glomerular filtration rate (GFR) ≥ 30 mL/min/1.73 m² using the 4-Variable Modification of Diet in Renal Disease (MDRD-4) variable formula (see [Appendix F](#))
8. Female subjects of childbearing potential have a negative pregnancy test at screening. Females of childbearing potential are defined as sexually mature women without prior hysterectomy or who have had any evidence of menses in the past 12 months. However, women who have been amenorrheic for 12 or more months are still considered to be of childbearing potential if the amenorrhea is possibly due to prior chemotherapy, anti-estrogens, or ovarian suppression.
9. Women of childbearing potential (ie, menstruating women) must have a negative urine pregnancy test (positive urine tests are to be confirmed by serum test) documented within the 24-hour period prior to the first dose of study drug.

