17.1. General Design

All data for enrolled subjects will be presented in data listings by subject number. For those summary tables in which baseline and change from baseline measurements will be presented, the last observed measurement prior to the initial dose of KD025 will be considered the baseline measurement.

Continuous data will be described using descriptive statistics: number of observations (*n*), mean, standard deviation, median, minimum and maximum. Frequencies and percentages will be used for summarizing discrete (categorical) data. When categorical data are presented, the percent will be suppressed when the count is zero in order to draw attention to the nonzero counts. The denominator for all percentages, unless otherwise specified, will be the number of subjects in the specified analysis population. Two-sided 95% confidence interval employing the exact binomial method will be provided for activity outcomes.

Hypothesis testing, if appropriate, will be carried out at the 5% (2-sided) significance level. Because of the exploratory nature of the study, no adjustments will be made for the multiplicity of endpoints. Nonparametric tests may be used in preference to parametric tests if parametric assumptions are notably violated. Missing values will not be imputed. If a subject does not have sufficient data for a particular analysis, they will be excluded from that analysis. Endpoints defined as an average of multiple measurements will be used those data points that are non-missing, and the denominator was adjusted accordingly.

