### **3.1.2 General Considerations**

General considerations for descriptive statistics and presentation for continuous and categorical data are given below.

Continuous data will be described using descriptive statistics: number of observations (n), mean, standard deviation, median, minimum, and maximum. Frequencies and percentages will be used for summarizing discrete (categorical) data. When categorical data are presented, the percent will be suppressed when the count is zero in order to draw attention to the nonzero counts. The denominator for all percentages, unless otherwise specified, will be the number of subjects in the cohort or in the specified analysis population.

Means, medians, standard deviations, and confidence intervals (CIs) will be reported to one decimal place more than the data reported on the case report form (CRF) or by the vendor. Minimum and maximum will be reported to the same number of decimal places displayed on the CRF or by the vendor. P-values will be reported to 4 decimal places.

Unless otherwise indicated, all summary tables will be presented by the following groups: Cohort 1 (KD025 200 mg QD PO), Cohort 2 (KD025 200 mg BID PO), Cohort 3 (KD025 400 mg QD PO), and Overall.

Because of the exploratory nature of the study, no adjustments will be made for the multiplicity of endpoints.

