## **3.2 Analysis Populations**

The following populations will be analyzed:

**Modified Intent-to-treat (mITT) Population:** The primary population for efficacy analyses will be a Modified Intent-to-treat (mITT) Population defined as all subjects who receive at least 1 dose of study medication. The mITT Population will be used for tables of demography, baseline characteristics, and efficacy.

**Responder Population:** The Responder Population is defined as subjects in the mITT population that achieved a PR or CR response at any post-baseline response assessment.

**Non-responder Population:** The Non-responder Population is defined as any subject in the mITT Population who is not a responder.

The responder and non-responder populations will be used for some subgroup analyses.

**Safety Population:** The Safety Population is defined as all subjects who receive at least 1 dose of study medication. In this study, the Safety Population is equivalent to the mITT Population.

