### 3.8.2.3 Response by Organ System

The database did not specifically capture baseline organ involvement. Organ involvement was determined as follows:

- All organs, except lungs:
  - If the baseline score is  $> 0$ , the organ will be defined as Involved, unless all response assessments are Not Evaluable (NE)
  - If the baseline score is 0, the organ will be defined as Not Involved, unless any response assessment of CR or PR which triggers clinical review to confirm baseline involvement.
- For the lungs:
  - If FEV1  $\geq 75\%$ , the organ will be defined as Not Involved
  - If FEV1  $< 75\%$ , the organ will be defined as Involved, unless all responses are NE

The response assessment for the 9 individual organs (skin, eyes, mouth, esophagus, upper GI, lower GI, liver, lungs, and joints and fascia) and global severity rating is categorized into 5 response status: CR, PR, Progression (P), NE, Stable (STB).

Number and percentage of subjects with best response of CR or PR and total (CR+PR) by individual organ system and global severity rating will be summarized and 2 series of percentages presented:

1. With the total number of subjects in the mITT Population with involvement of the given organ at baseline as denominator
2. With the number of subjects in the Responder Population with involvement of the given organ at baseline as denominator

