**Table 5. Efficacy TLFs**

T/F/L	Title	Population
Primary Endpoint: ORR		
T	Overall Response Rate	mITT
T	Best Overall Response	mITT
L	Listing of Overall Response by subject by visit	mITT
Secondary Endpoint: DOR		
T	Descriptive Kaplan-Meier and landmark statistics for primary DOR	Responder
F	Kaplan-Meier plot of primary DOR	Responder
L	Listing of all primary DOR episodes for each subject	Responder
T	Descriptive Kaplan-Meier and landmark statistics for secondary DOR	Responder
F	Kaplan-Meier plot of secondary DOR	Responder
L	Listing of all secondary DOR episodes for each subject	Responder
T	Descriptive Kaplan-Meier and landmark statistics for tertiary DOR	Responder
F	Kaplan-Meier plot of tertiary DOR	Responder
L	Listing of all tertiary DOR episodes for each subject	Responder
T	Descriptive Kaplan-Meier and landmark statistics for quaternary DOR	Responder
F	Kaplan-Meier plot of quaternary DOR	Responder
L	Listing of all quaternary DOR episodes for each subject	Responder
Secondary Endpoint: TTR		
T	Descriptive statistics for time to response (TTR) and cumulative response rate over time	Responder
L	Listing of TTR for each subject	Responder
Secondary Endpoint: Response by Organ System		
T	Best response by individual organ	mITT
T	Best response by individual organ	Responder
L	Listing of organ score and response assessment by subject and visit	mITT
T	Descriptive statistics for time to response (TTR) and cumulative response rate over time by organ	mITT
T	Descriptive statistics for time to response (TTR) and cumulative response rate over time by organ	Responder
Secondary Endpoint: TTNT		
T	Descriptive Kaplan-Meier and landmark statistics for TTNT	mITT
F	Kaplan-Meier plot for TTNT	mITT
Secondary Endpoint: Corticosteroid Dose		
T	Descriptive statistics for prednisone equivalent dose of corticosteroids	mITT Responder

T/F/L	Title	Population
		Non-responder BL corticosteroid dose level (upper and lower 50 th percentiles)
T	Summary of raw and change from baseline on prednisone equivalent dose of corticosteroids by visit	mITT Responder Non-responder BL corticosteroid dose level (upper and lower 50 th percentiles)
L	Listing of all the steroid raw and standardized dosing by subject and visit	mITT
Secondary Endpoint: CNI Dose		
T	Summary of descriptive statistics for CNI	mITT
L	Listing of all the CNI dosing by subject and visit	mITT
Secondary Endpoint: FFS		

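### The CNI reduction and discontinuation percentages have no at-risk denominator, so by default they are taken over all treated subjects, including those who never had a CNI to reduce

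*SAP*

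**What the plan says.** SAP 3.8.2.6 defines two summaries: "Number and percentage of subjects who reduced CNI dose" and "Number and percentage of subjects who ever discontinued CNI during KD025 treatment period". It states no denominator for either, and only the second carries a treatment-period window.

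SAP 3.1.2 supplies the default: "The denominator for all percentages, unless otherwise specified, will be the number of subjects in the cohort or in the specified analysis population". Protocol 17.1 has nearly the same rule: "The denominator for all percentages, unless otherwise specified, will be the number of subjects in the specified analysis population".

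SAP Table 5 lists "Summary of descriptive statistics for CNI" with mITT as its population. SAP 3.2 describes that set as a "Modified Intent-to-treat (mITT) Population defined as all subjects who receive at least 1 dose of study medication", with no condition on CNI use.

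Protocol 7.2, criterion 2, admits subjects "Receiving glucocorticoid therapy and calcineurin therapy or glucocorticoid therapy alone for cGVHD at study entry". Protocol Section 15 repeats that a CNI is optional.

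For organ response the SAP does write a restricted denominator (3.8.2.3): "With the total number of subjects in the mITT Population with involvement of the given organ at baseline as denominator".

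**The concern.** A subject who is never on a CNI cannot reduce or stop one. Under the default rule this subject still counts in the percentage, and always on the side of no change. The corticosteroid summaries in SAP 3.8.2.5 are built in much the same way but do not share the problem, because every eligible subject must be on a glucocorticoid at entry.

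Change in corticosteroid and CNI dose is a named secondary endpoint, and tables are shown by cohort and overall. The figure as planned combines two quantities: how often users came off or lowered the drug, and what share of the cohort used it at all. Someone reading across the three dose cohorts could not tell which of the two had moved.

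**Working it through.** **Step 1. Which denominator applies.** SAP 3.8.2.6 is silent, so the default in SAP 3.1.2 governs. Table 5 names mITT, and SAP 3.2 makes mITT every treated subject. With about 16 subjects per cohort (SAP 2.2), the denominator is about 16.

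**Step 2. Whether another rule removes non-users.** SAP 3.1.5 drops subjects with missing data from categorical percentages. A subject recorded as not taking a CNI has a known status, not a missing one, and no text applies the rule to non-users.

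**Step 3. The arithmetic.** The plan gives no figure for these percentages, so there is none to reproduce. Let N be the cohort size, u the number who ever use a CNI, and r the proportion of those who reduce (or stop) it.

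Reported percentage = (u × r) / N = (u / N) × r

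This is below r whenever u < N. If nobody starts a CNI on study, u is the number on a CNI at entry. Starters who later reduce or stop would also enter the numerator, so u is then larger than the entry count.

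**Step 4. Illustration.** Assumptions: N = 16, r = 50%, no on-study starts. The values of u are assumed, because the documents give none.

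| Users u | Who reduce | Over all 16 | Over users |
|---|---|---|---|
| 6 | 3 | 3/16 = 18.8% | 3/6 = 50% |
| 8 | 4 | 4/16 = 25.0% | 4/8 = 50% |
| 10 | 5 | 5/16 = 31.3% | 5/10 = 50% |
| 16 | 8 | 8/16 = 50.0% | 8/16 = 50% |

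The cohorts with 6 and 10 users differ by 31.3 − 18.8 = 12.5 points (2/16), although the rate among users is the same.

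**Step 5. How plausible a gap of that size is.** Suppose each subject independently has probability p of being on a CNI at entry, with p between 30% and 70% (an assumption). For two cohorts of 16, sum the product of the two binomial probabilities over all pairs of counts that differ by at least 4:

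- p = 0.3 or 0.7: 0.175
- p = 0.5: 0.215

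The probability is therefore about 0.18 to 0.22 for any given pair of cohorts. A gap of 8 or more, such as 4 against 12 users, has probability of only 0.003 to 0.007.

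**Step 6. The window.** The discontinuation summary is limited to the KD025 treatment period and the reduction summary is not. In SAP 3.8.2.5 the corresponding corticosteroid summaries both carry that limit. Protocol Table 1 collects concomitant medications only until 28 days after the last dose, so little off-treatment dose detail could enter.

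**The case against.** The best reply has four parts.

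- **The mITT denominator is inferred.** SAP 3.8.2.6 does not state it, and the population column of Table 5 is weak evidence. That column also says mITT for best response by organ, where 3.8.2.3 restricts the denominator, and for DOR by subgroup, although DOR is reported only for responders. This is fair as far as Table 5 goes. The default in SAP 3.1.2 still applies unless something else is specified, and here nothing is. The organ-response text shows that the SAP writes an at-risk denominator when it wants one.
- **No information is lost.** Table 4 plans a CNI summary by cohort and a listing by subject, Table 5 lists CNI dosing by subject and visit, and counts are reported beside percentages. A reader could therefore rebuild the rate among users. This stands as mitigation, but the tabulated percentage would remain the diluted one.
- **The analysis is only descriptive.** No between-cohort test of CNI change is planned, and the share of all treated subjects who came off a CNI is a legitimate quantity, if a less useful one. This also stands, and it limits the weight of the point.
- **The cohorts are sequential.** Any comparison across them is already open to differences in entry mix, and a smaller denominator does not cure that. This is true. The change removes one known source of distortion and does not make the cohorts comparable.

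A reader might go further and infer that the cohorts did differ in CNI use, or that the table will show a large spurious dose effect, for instance 12.5% against 37.5% from 4 and 12 users at a 50% rate. The documents do not support that. They give no CNI-use counts, and a gap of that size would be very unlikely under random entry use.

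**Conclusion.** The point holds as a denominator defect in one descriptive secondary-endpoint table. Followed as written, the SAP divides by all treated subjects, so the percentage understates the rate among users whenever some subjects never use a CNI, and it varies with the cohort's entry mix.

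The size cannot be fixed from the documents. It is nil if every subject enters on a CNI and grows as the share of users falls. The 18.8% and 31.3% in the illustration rest on assumed user counts, an assumed 50% rate and no on-study starts. The probability of 0.18 to 0.22 rests on independent entry use between 30% and 70%. The primary endpoint and the sample size are untouched. The missing window on the reduction summary is minor.

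**What to change.** In SAP 3.8.2.6 and in the CNI row of Table 5:

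- Set the denominator for both percentages to mITT subjects receiving systemic tacrolimus or cyclosporine at C1D1, and show that n for each cohort and overall.
- Count subjects who start a CNI on study separately, outside these percentages.
- As a minor alignment with 3.8.2.5, limit both summaries to the KD025 treatment period.

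This takes a short addition to the text and a table footnote, and no new data, because CNI dosing is already listed by subject and visit. The cost is precision. Protocol 17.1 provides exact 95% intervals for activity outcomes, and on the assumed 8 users with 4 reductions the interval would go from 7.3% to 52.4% (4/16) to 15.7% to 84.3% (4/8). The wider interval reflects how few subjects carry information on this endpoint.

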### **3.8.2.7 Failure-free Survival (FFS)**

Failure-free survival will be defined as the time from first dose of study drug to either the start of another new systemic treatment for cGVHD, relapse of the underlying

disease (both will be defined by clinical team review), or death. If no such events happen, FFS will be censored by last response assessment or long term follow up assessment, whichever is the latest and available. Failure-free survival will be analyzed by the Kaplan-Meier survival method as well as the landmark analyses at 6, 12, 18, and 24 months. In addition, analyses for the three components of FFS will also be provided.

#### **3.8.2.8 Overall Survival (OS)**

Overall survival will be defined as the time from first dose of study drug to death due to any reason. If there is no death, OS will be censored by last visit, last long term follow up, or study cutoff date, whichever is the latest. OS will be analyzed by the Kaplan-Meier survival method as well as the landmark analyses at 6, 12, 18, and 24 months.

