8.8. Long-Term Follow-Up

Subjects will be contacted approximately every 8 weeks and can be contacted via telephone, email or postal mail to confirm survival status and the initiation of any anti-cancer treatment or any changes in treatment of cGVHD. This can also be confirmed from electronic medical records.

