13.1. Subjects' Decision to Withdraw

Subjects have the right to withdraw from the study at any time and for any reason without prejudice to their future medical care by the physician or at the institution.

Subjects can decline to continue receiving study drug and/or other protocol-required therapies or procedures at any time during the study. If this occurs, the investigator is to discuss with the subject the appropriate processes for discontinuation from study drug or other protocol-required therapies and must discuss with the subject the options for continuation of the Schedule of Assessments ([Table 1](#)) and collection of data, including endpoints and adverse events.

Withdrawal of consent for a study means that the subject does not wish to receive further protocol-required therapies or procedures, and the subject does not wish to or is unable to continue further study participation. Subject data up to withdrawal of consent will be included in the analysis of the study, and where permitted, publically available data can be included after withdrawal of consent. The investigator is to discuss with the subject appropriate procedures for withdrawal from the study.

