13.1.2 Study Termination

Reasons for study termination include:

- Completion of follow-up period
- Voluntary withdrawal by subject
- Subject lost to follow-up
- Termination of the study by sponsor
- Subject death

In the event of premature discontinuation of treatment, subjects must return to the clinic to complete the EOT Visit and 28-Day Follow-Up assessments. Refer to [Section 8.5](#) for a complete list of procedures to be performed at these visits. If a subject dies, Kadmon Corporation will actively seek to know the date of death.

If there is an ongoing toxicity because of KD025, subjects must be followed with appropriate medical management until resolution or stabilization.

A reasonable effort should be made to contact any subject lost to follow-up during the course of the study in order to complete assessments and retrieve any outstanding data. If the subjects are unreachable by telephone after 3 attempts, a certified registered return receipt letter should be sent requesting that contact be made with the investigator to report survival information.

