### 3.8.2.4 Time to Next Therapy (TTNT)

The TTNT will be measured as the time from first treatment to the time of new systemic cGVHD treatment (which will be defined by clinical team review), censored by last response assessment or long term follow up assessment, whichever is the latest and available. TTNT will be analyzed by the Kaplan-Meier survival method as well as the landmark analysis at 6, 12, 18, and 24 months.

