### **3.14 Primary CSR Analysis**

A primary CSR analysis will be conducted 1 year after the last subject is enrolled.

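### The OS censoring rule can never return a date before the study cutoff, so a subject lost or withdrawn earlier is counted as alive to cutoff and OS can be overstated

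*SAP*

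**What the plan says.** SAP 3.8.2.8 sets the endpoint: "Overall survival will be defined as the time from first dose of study drug to death due to any reason". Without a death, "OS will be censored by last visit, last long term follow up, or study cutoff date, whichever is the latest". The analysis is Kaplan-Meier with landmarks at 6, 12, 18 and 24 months. Protocol 17.4 defines OS with the same origin and event and gives no censoring rule, so nothing there overrides the SAP.

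The SAP does not define the cutoff date. SAP 3.14 gives only the timing: "A primary CSR analysis will be conducted 1 year after the last subject is enrolled".

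Two neighbouring endpoints are handled differently. For FFS (SAP 3.8.2.7), "FFS will be censored by last response assessment or long term follow up assessment, whichever is the latest and available". TTNT (SAP 3.8.2.4) is likewise "censored by last response assessment or long term follow up assessment, whichever is the latest and available". Neither lists the cutoff date.

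The protocol foresees both withdrawal and loss to follow-up (13.1.2) and makes efforts to learn survival status:

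- Section 8.8 provides for contact about every 8 weeks and adds: "This can also be confirmed from electronic medical records".
- Section 13.1 allows that "where permitted, publically available data can be included after withdrawal of consent".
- Section 13.1.2 says that, after three failed telephone attempts, "a certified registered return receipt letter should be sent requesting that contact be made with the investigator to report survival information". It also commits the sponsor to seek the date of any death.

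**The concern.** Kaplan-Meier estimation needs each subject without an event to leave the risk set when observation for that event stops. This rule keeps them in until cutoff, even if survival was last confirmed long before. An unknown status is treated as alive.

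The direction is fixed. For the same recorded deaths, later censoring can only enlarge the risk set n in each factor 1 − d/n, so the curve can only stay the same or rise. The larger risk sets also make the standard errors too small. The error grows with time, so the 18 and 24 month landmarks are the most exposed. If a lost subject dies and the death is never recorded, the result is upward bias against true survival, in a favourable direction, on a named secondary endpoint.

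**Working it through.** **No plan figure to reproduce.** The documents give no expected OS, loss rate or event count. All rates below are assumptions, shown as ranges.

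**Step 1: what the rule returns.** Censoring date = max(last visit, last long-term follow-up, cutoff). With an illustrative cutoff of 1 January 2020, a subject last seen on 1 March 2018 and last contacted on 1 April 2018 is censored on 1 January 2020, 21 months after last known alive. If contacts after the cutoff stay in the data, the maximum can fall later than the cutoff, but never earlier.

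**Step 2: a hand example.** Take 16 subjects with deaths at months 8 and 14 and all others either lost at month 5 or followed past 24 months. This shows that the two rules differ; it does not estimate bias.

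| Lost at month 5 | SAP rule | Last known alive |
|---|---|---|
| 1 | 15/16 × 14/15 = 87.5% | 14/15 × 13/14 = 13/15 = 86.7% |
| 3 | 15/16 × 14/15 = 87.5% | 12/13 × 11/12 = 11/13 = 84.6% |

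**Step 3: bias when no death is recorded after loss.** Assume exponential death (rate a) and independent exponential loss (rate b), with a = −ln(OS at 24 months)/24 and b = −ln(1 − proportion lost by 24 months)/24. Only deaths that precede loss are recorded, so under the rule

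KM(t) → 1 − a/(a+b) × (1 − exp(−(a+b)t)), while the truth is exp(−at).

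For OS 80% and 20% loss, a = b and exp(−24(a+b)) = 0.80 × 0.80 = 0.64. The rule gives 1 − 0.5 × 0.36 = 82.0% against a true 80.0%, a bias of 2.0 points.

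Bias at 24 months, in percentage points:

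| True 24-month OS | 5% lost | 10% | 20% | 30% |
|---|---|---|---|---|
| 90% | 0.25 | 0.50 | 1.02 | 1.56 |
| 80% | 0.49 | 0.98 | 2.00 | 3.07 |
| 70% | 0.71 | 1.44 | 2.93 | 4.50 |

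Over the same grid the range is 0.02 to 0.36 points at 6 months, 0.06 to 1.33 at 12 and 0.14 to 2.75 at 18. With no loss it is 0.

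**Step 4: partial capture.** If half of the deaths after loss are found, the unrecorded deaths halve and so does each figure: 0.12 to 2.25 points at 24 months.

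**Step 5: simulation.** The setting is n = 48, an assumed 24-month uniform accrual and a cutoff 12 months after the last enrolment. The 24-month differences were 0.24 to 4.51 points, in line with the closed form. Censoring at the last date known alive was essentially unbiased under independent loss (for OS 80% and 20% loss: 80.0%, against 82.0% under the rule). The ratio of Greenwood standard errors, rule to last-known-alive, was 0.83 to 0.98, so the rule's standard error is 2 to 17% too small. The last-known-alive standard error itself was 4.6 to 8.0 points.

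**The case against.** **The replacement rule has its own bias.** If some deaths after last contact are added from records while survival is not, censoring at the last date known alive errs downward by nearly the same amount. With half of later deaths captured, OS 80% and 20% loss, the SAP rule is about 1.0 point too high and the alternative about 1.0 point too low. This stands. Changing the sentence alone is a clear gain only when few later deaths are found; otherwise deaths and survival must be sought from the same sources.

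**Ascertainment is the deeper issue.** If every death were found, the existing rule would be unbiased. That is true, but the tracing provisions are efforts. None requires survival to be confirmed for every subject at cutoff, and when they fail the rule records the subject as alive. When they succeed for everyone, the corrected rule gives the same dates as the present one.

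**Withdrawal is partly covered.** Protocol 13.1 includes data up to withdrawal of consent, which arguably limits the survival time credited afterwards. It sets no censoring date and does not reach subjects lost to follow-up.

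**The comparison with FFS and TTNT is weak.** Relapse and new therapy need an assessment or contact to be detected, while death can be learned passively. The comparison is therefore supporting evidence only.

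**The effect is small.** Every rate is assumed, a loss of up to 30% has no basis in the documents, and a subject still in regular contact gains only about 8 weeks. All of this is fair and limits the weight of the point. It does not make the rule correct.

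**Conclusion.** The concern holds. As written, the rule cannot censor before the cutoff, and no other section makes an exception for lost or withdrawn subjects. The direction relative to last-known-alive censoring is certain. Bias against true survival requires at least one subject whose status becomes unknown before cutoff and whose later death goes unrecorded.

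The sizes rest on constant hazards, loss unrelated to prognosis and the assumed rates. If subjects who leave are at higher risk of death, the overstatement is larger than shown. In all scenarios examined it stays below one standard error at n = 48. ORR, dose escalation and the stopping rules do not depend on it. It should be fixed because the error favours the drug and the correction is standard.

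**What to change.** Replace the censoring sentence in SAP 3.8.2.8 with: *Subjects with no recorded death are censored at the last date known alive (the latest of last visit, last long-term follow-up contact, or confirmation of survival from medical or public records), not later than the study cutoff date.* Subjects confirmed alive at cutoff are still censored there. Define the cutoff date.

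Apply the record check to every subject without a recorded death, within the limits of consent, so that deaths and survival come from the same sources.

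The SAP change is one sentence and one derivation. The record check is additional work for roughly 10 sites, using sources the protocol already allows. OS estimates will be equal or slightly lower and the intervals somewhat wider. Bias from informative loss is reduced, not removed. Without the uniform record check, the downward error with half of later deaths captured would be about 0.2 to 2.1 points at 24 months.
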